### **3.6 Treatment Compliance**

Patients will keep a pill diary.

### **3.7 Precautions and Restrictions**

- Fluid deficits should be corrected before and throughout treatment.

### **3.8 Contraception Requirements**

The effects of MLN9708 on human pregnancy or development of the embryo or fetus are unknown. Therefore, female patients participating in this study should avoid becoming pregnant, and male patients should avoid impregnating a female partner. Nonsterilized female patients of reproductive age and male patients should use effective methods of contraception through defined periods during and after study treatment as specified below.

Female patients must meet the following eligibility criteria:

- Are postmenopausal for at least 1 year before the screening visit, OR
- Are surgically sterile, OR
- Agree to completely abstain from heterosexual intercourse
- If they are of childbearing potential, agree to practice 2 effective methods of contraception, at the same time, for at least 30 days before starting study drug through 28 days after the last dose of study treatment.
  - The 2 methods of reliable contraception must include 1 highly effective method and 1 additional effective (barrier) method. Females of childbearing potential must be referred to a qualified provider of contraceptive methods if needed. The following are examples of highly effective and additional effective methods of contraception:

Highly effective methods:

- Intrauterine device (IUD)
- Hormonal (birth control pills, injections, implants)

- Tubal ligation
- Partner's vasectomy

Additional effective methods:

- Male condom
- Diaphragm
- Cervical Cap

Male patients, even if surgically sterilized (ie, status postvasectomy), must meet the following eligibility criteria:

- Agree to completely abstain from heterosexual intercourse, OR
- Agree to practice effective barrier contraception during the entire study treatment period and through 28 days after the last dose of study treatment if their partner is of childbearing potential, even if they have had a successful vasectomy.

### **3.9 Duration of Treatment and Patient Participation**

. Patients will be informed that they have the right to withdraw from the study at any time for any reason, without prejudice to their medical care. Patients will be removed from study for the following reasons.

- Progression of disease
- Patient's request to withdraw from the study or refusal of further therapy
- Unacceptable toxicity
- Pregnancy
- Physicians discretion
- Lost to long term follow up after 12 months of no contact

#### **Definition of Progressive Disease:**

Progressive disease (for patients not in CR) requires one or more of the following:

- >25% increase in the level of the serum monoclonal paraprotein, which must also be an absolute increase of at least 0.5 g/dL and confirmed by at least one repeated investigation.
- >25% increase in the 24 hour urinary light chain excretion, which must also be an absolute increase of at least 200 mg/24 hour and confirmed by at least one repeated investigation.
- >25% increase in plasma cells in a bone marrow aspirate or trephine biopsy, which must also be an absolute increase of at least 10%.
- Definite increase in the size of existing bone lesions or soft tissue plasmacytomas.

- Development of new bone lesions or soft tissue plasmacytomas (development of a compression fracture does not exclude continued response).
- Development of hypercalcemia (corrected serum calcium > 11.5 mg/dL or 2.8 mmol/L) not attributable to any other cause.

Relapsed disease (for patients who were in CR) requires at least one or more of the following (to be used for analyzing disease free survival).

- Reappearance of serum or urine monoclonal paraprotein by immunofixation or electrophoresis.
- Development of at least 5% plasma cells in the bone marrow.
- A difference between involved and unininvolved FLC levels of >10 mg/dL, only in patients without measurable paraprotein in the serum and urine.
- Development of new lytic bone lesions or soft tissue plasmacytomas or definite increase in the size of residual bone lesions (development of a compression fracture does not exclude continued response and may not indicate progression).
- Development of hypercalcemia (corrected serum calcium > 11.5 g/dL or 2.8 mmol/L) not attributable to any other cause.
- Appearance of any other sign of progression.

Patients with relapsed disease (recurrence of disease after attaining a CR) should continue on treatment if they do not fulfill criteria for progressive disease. This would apply to patients at any time following initiation of maintenance therapy.

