### Analysis plan, Sample Size and Power

The primary endpoint is PFS, defined as the time from autologous stem cell transplantation (ASCT) to the time of clinical progression, death, whichever occurs first or the time of last contact. It is hypothesized that the combination will prolong PFS compared to the current standard regimen. A total of 48 patients (dosed at 3 mg of Ixazomib) will be enrolled at an accrual rate of 2 patients per month over 24 months. Additional 48 months of follow-up is planned after the last patient is recruited into the trial. Assuming that PFS time follows an exponential distribution, and patients treated with the current standard regimens had a median PFS of 40 months, we will monitor the PFS using the method of Thall et al. (Thall, 2005). Let  $T_s$  and  $T_e$  represent the time to progression for the standard regimens and the proposed treatment regimen, respectively. We assume  $T_s|M_s$  and  $T_e|M_e$  follow an exponential distribution with respective median  $M_s$  and  $M_e$ . Furthermore, we assume that the prior for  $M_s$  follows an inverse gamma distribution  $IG(100, 3960)$  to reflect our knowledge of PFS for the patients treated with the standard regimens. This has a mean of 40 months, and a variance of 16.3. The prior for  $M_e$  is assumed to be  $IG(3, 80)$ , which has the same mean of 40 months and a larger variance of 1600 to reflect the uncertainty about the median PFS of the proposed treatment regimen.

The PFS will be monitored every six months, and the study will be terminated early if there is little evidence based on the available data that the median PFS of the patients treated with the proposed treatment regimen is 12 months or more than that of the patients treated with the standard regimens. The formal stopping rule is

$$\Pr(M_e > M_s + 12 \mid \text{data}) < 0.035$$

Specifically, the trial will be stopped early if there is less than 3.5% chance that the median PFS for the patients treated with the proposed treatment regimen is 12 months or more than the median PFS for the patients treated with the standard regimens. The probability cutoff 0.035 was chosen to obtain an early stopping probability around 10% (0.091) if the true median PFS for the proposed treatment regimen results in a 12 months improvement over the historical median PFS of 40 months.

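### Does the plan leave open which progression list dates a PFS event, and must serum free light chains count for patients not in CR?

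*Combined protocol and SAP*

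**What the plan says.** Section 5 (Analysis plan, Sample Size and Power) runs PFS from transplant "to the time of clinical progression, death, whichever occurs first or the time of last contact". It does not refer to section 3.9. The same section calls the monitored variable time to progression.

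Section 3.9 places two lists under "Definition of Progressive Disease". The first begins "Progressive disease (for patients not in CR) requires one or more of the following" and covers serum paraprotein, 24-hour urinary light chain, marrow, bone or plasmacytoma, and calcium. The second is for patients who were in CR and is marked "to be used for analyzing disease free survival". It includes "Reappearance of serum or urine monoclonal paraprotein by immunofixation or electrophoresis", its only FLC item is "A difference between involved and unininvolved FLC levels of >10 mg/dL, only in patients without measurable paraprotein in the serum and urine", and it ends with "Appearance of any other sign of progression". A closing sentence says that patients who relapse after CR "should continue on treatment if they do not fulfill criteria for progressive disease", and applies this at any time after maintenance starts.

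Disease-free survival appears neither in the objectives (sections 2.1 and 2.2) nor in section 5. Section 3.10.1 bases efficacy evaluation on serum and urine myeloma protein, marrow, skeletal survey and plasmacytomas, and adds that a FreeLite sample is taken. The flow chart in section 8.1 schedules it every 1-3 cycles.

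**The concern.** PFS is the primary endpoint and the only efficacy input to the six-monthly futility rule. If two analysts could choose different lists, the same patient could carry two event dates and the same data could lead to different stopping decisions. The relapse list is met at lower thresholds, so for patients in CR it would usually give the earlier date. Patients in CR are expected: section 1.1 discusses them, and section 2.2 counts stringent CR among the responses.

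The second worry is narrower. A patient not in CR whose disease can be followed only by serum FLC has no FLC event under either list, so progression might be dated late. Eligibility (sections 3.2.1 and 3.2.2) does not exclude such patients.

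**Working it through.** **The two lists side by side**

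| Item | Progression list | Relapse-from-CR list |
|---|---|---|
| Paraprotein | rise above 25% and at least 0.5 g/dL in serum (200 mg/24 h in urine), confirmed | any return on immunofixation or electrophoresis |
| Marrow plasma cells | rise above 25% and at least 10% absolute | 5% |
| Bone, plasmacytoma, calcium | listed | listed |
| Serum FLC | not listed | difference above 10 mg/dL, if no measurable paraprotein |
| Stated use | progressive disease | disease-free survival |

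**Which list dates PFS?**

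1. The relapse list is assigned to a named endpoint that is not PFS.
2. The closing sentence of section 3.9 judges patients who relapsed from CR by the progressive-disease criteria, so the protocol itself uses the first list for them.
3. The first list's restriction to patients not in CR does not block this. A patient whose paraprotein has returned is no longer in CR, so by the time the higher threshold can be reached the heading fits.
4. The monitoring model's variable is time to progression, the event that the first list defines.

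All four point to the progression list.

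**What would the other reading cost?** Assume exponential PFS with median 40 months (section 5), λ = ln 2/40 = 0.01733. If a share f of patients has the event dated d months later, the survival curve from month d on is (1 − f)·exp(−λt) + f·exp(−λ(t − d)). Setting this to 0.5 gives

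median = 40 + ln(1 − f + f·exp(λd))/λ.

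Example: f = 0.20, d = 6: exp(0.1040) = 1.1096; ln(1.0219)/0.01733 = 1.25; median 41.25.

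| Share f | d = 3 | d = 6 | d = 12 |
|---|---|---|---|
| 5% | 40.15 | 40.32 | 40.66 |
| 10% | 40.31 | 40.63 | 41.32 |
| 20% | 40.61 | 41.25 | 42.61 |
| 30% | 40.92 | 41.87 | 43.87 |
| 50% | 41.52 | 43.08 | 46.31 |

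Every f and d is an assumption. For the choice of list in CR patients I took 20-50% (about 10-24 of 48); for FLC in patients not in CR, 5-20% (about 2-10 of 48). The model also delays deaths, so each cell is an upper bound for its own inputs.

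**Scale.** With 48 patients entering evenly over 24 months and 48 more months of follow-up, individual follow-up runs from 48 to 72 months. The mean event-free probability is (exp(−48λ) − exp(−72λ))/(24λ) = (0.4353 − 0.2872)/0.4159 = 0.356. Expected events are 48 × 0.644 = 30.9, and the standard error of the median is about 40/√31 = 7.2 months. The largest FLC shift, 2.61 months, is 0.36 of that.

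**Futility rule.** The priors check: 3960/99 = 40 with variance 40²/98 = 16.3, and 80/2 = 40 with variance 40²/1 = 1600. Simulating the rule with six-monthly looks during accrual and one final look 48 months after the last entry gives stopping probabilities of 0.916, 0.635, 0.428, 0.166, 0.107 and 0.052 at medians 30, 36, 40, 48, 52 and 60. Table 1 states 0.92, 0.64, 0.41, 0.16, 0.091 and 0.053, so it is reproduced to within 2 points. Six-monthly looks throughout follow-up, which is the literal text, give 0.517 at 40.

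Stopping shifts from a delay are poor evidence here. Take median 40, 20% delayed by 6 months, and looks at months 6, 12, 18 and 72. Stopping falls from 0.416 (0.181 at months 6-18 plus 0.235 at month 72) to 0.328 (0.112 plus 0.216). Of the 0.088 fall, 0.069 arises at months 6-18, where the model keeps every delayed patient event-free, deaths included, for the first 6 months. The month-72 part falls by only 0.019, and a stop at that point saves no patient and no follow-up.

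**The case for a change.** The strongest opposing case is that all of this is inference. The closing sentence of section 3.9 governs whether treatment continues and says nothing about endpoint dating. Read literally, the progression list excludes patients in CR. The relapse list's last item, "Appearance of any other sign of progression", can be taken to mean that its other items are progression too. And an unclear primary event is hard to repair credibly once results have been seen, while naming the list costs one sentence.

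Part of this stands. Section 5 lacks a cross-reference, the heading is loose, and the disease-free-survival label points to an endpoint the plan never analyses. But an orphan label does not make the relapse list a rival for PFS; it shows that the list was meant for something else. Counting relapse as a PFS event means overriding the list's stated use. Counting progression needs only the observation that a relapsed patient is no longer in CR.

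The FLC omission is also real. For patients not in CR, though, nothing is contradictory: their list applies by its own heading and still dates events by urinary light chain, marrow, bone, plasmacytoma and calcium. Drawing a FreeLite sample does not make it part of the endpoint. The documents do not show that any such patient lacks measurable serum and urine paraprotein, and the existing FLC item is a level that a patient not in CR could already exceed at baseline, so it could not simply be carried over. A supportive analysis with an FLC event fixed in advance is open to the sponsor, but the plan does not need it.

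**Conclusion.** No change to the plan is called for. On which list applies, this is a clerical gap that analysts would fill sensibly from section 3.9: the progression list dates PFS for all patients, and relapse from CR alone is not an event. On that reading no event date is in doubt. On FLC, the omission is a defensible choice of criteria with little to gain from altering it: 0.15 to 2.61 months on a 40-month median, if 5-20% of patients are affected by 3-12 months, against a standard error of about 7.2 months.

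If the relapse list had been meant after all, the median on the progression list would be 0.61 to 6.31 months longer (20% with 3 months to 50% with 12 months). The upper end is not trivial, but it rests on shares and delays that the documents do not give. Whether either effect would favour the regimen is also unknown, because the progression criteria behind the 40-month benchmark are not stated.

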## 3.10 Efficacy, Correlative Studies, and Safety Measurements

### 3.10.1 Efficacy Measurements

Patients will be staged every 1-3 cycles +/- 7 days while on protocol. Efficacy evaluations will be based on changes in myeloma protein measurements in serum and 24-hour urine, bone marrow examination as indicated, skeletal survey as indicated clinically, extramedullary plasmacytomas as clinically indicated. A serum sample for FreeLite™ testing will be obtained.

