### **3. INVESTIGATIONAL PLAN**

#### **3.1 Overall Design and Plan of the Study**

Eligible patients will be enrolled and maintenance therapy on protocol no less than 60 days and must be initiated no more than 180 days post ASCT.

Patients will have standard restaging studies prior to initiation of therapy.

Standard post transplant therapy per institutional guidelines will be unaltered including prophylaxis therapy, vaccinations and restaging.

Patients who have completed ASCT and meet eligibility criteria will initiate maintenance therapy based on time on enrollment either in the phase dose escalation or expansion portion of trial.

Patients' clinical laboratory values and toxicity must be as specified below within 5 days before the first dose of study drug:

- Platelet count  $\geq 100,000/\text{mm}^3$
- Neutrophil count  $\geq 1000/\text{mm}^3$  (No growth factors within 5 days)
- Total bilirubin  $\leq 1.5 \times \text{ULN}$
- Alanine aminotransferase (ALT) and aspartate aminotransferase (AST)  $\leq 3 \times \text{ULN}$
- Creatinine  $< 2.5 \text{ mg/dL}$

Recovered (ie,  $\leq$  Grade 1 toxicity) from the reversible effects of autologous stem cell transplant.

Each cycle will be defined as a 28 day cycle. Drug holidays and break in therapy including those due to holidays, physician discretion and drug delivery are allowed as needed. Study drug will begin at Lenalidomide (10 mg/day); after three cycles , provided the ANC is  $\geq$  1000/ $\mu$ L, platelet count  $\geq$  100,000/ $\mu$ L, and all nonhematologic toxicity is  $\leq$  grade 1, then the dose may be increased to 15 mg/day at discretion of physician.

MLN 9708 will be dosed at 3 mg flat dose on days 1, 8, 15 administered orally.

Patients will be allowed to receive radiotherapy for palliation of symptoms during the course of maintenance therapy

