**3.3.3.1 Criteria for Beginning or Delaying a Subsequent Treatment Cycle**

Treatment with Lenalidomide and MLN9708 will use a cycle length of 28 days. For a new cycle of treatment to begin, the patient must meet the following criteria:

- ANC must be  $\geq$  1,000/mm^3.
- Platelet count must be  $\geq$  75,000/mm^3.

In addition, all other toxicity considered to be related to treatment with MLN9708 must have resolved to  $\leq$  Grade 1, to the patient's baseline values, or to a level considered acceptable by the physician (eg, hypokalemia that can be managed by replacements) before a new cycle of MLN 9708 treatment may begin.

If greater than  $> 4$  week delay in starting subusequent cycle due to recovery from toxicity, consider dose reduction in attributable drug.

If the patient fails to meet the above-cited criteria for initiation of the next cycle of treatment, dosing should be delayed until recovery. The maximum delay before treatment should be discontinued will be 6 weeks or at the discretion of the Principal Investigator.

Intracycle dosing :

Lenalidomide should be held if plt < **If platelet count  $\leq 30 \times 10^9/\text{L}$  or ANC  $\leq 0.75 \times 10^9/\text{L}$**   
**If platelet count  $\leq 30 \times 10^9/\text{L}$  or ANC  $\leq 0.75 \times 10^9/\text{L}$  until recovered to platelet > 75,000 and ANC > 1.0**

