## 8. APPENDICES

### 8.1 Study Flow Chart

Procedure	Screening ≤ 28 days from Initiation of therapy (may include Day 1)	Baseline	Cycle 1: (except cycle 1 day 1  ) 			all cycles beyond cycle 1		End of study	Follow up
			Cycle 1 Day 1 +/- 7 days	Day 8 +/-3 days (only dose escalation phase)	Day 15 +/-3 days ( only dose escalation phase)	Day 1 +/-7 days			
Informed consent	X								
Inclusion/Exclusion criteria	X								
Complete Medical Hx	X								
Confirmation Dx and status of disease and prior Rx	X								
MDASSI Questionnaire and Correlative Samples 		X					X 		
Record concurrent therapies/procedures	X								
Record adverse events	X	X					X	X	
Physical examination, vital signs Score 	X	X	X	X			X	X	
Skeletal survey( as clinically indicated)	X							X	
Bone Marrow aspiration and biopsy	X						X 	X	
12 Lead ECG	X								
Hematology 	X 	X	X	X			X	X	
Serum chemistry 	X 	X	X	X			X	X 	
TSH	x								
Ht, Wt, BSA	X	X					X	X	
Pregnancy test for females of child bearing potential	X	X 					X 	X	
Register Patient into Rev Assist® Program	X								
Serum and urine M component quantification	X						X (every 1-3 cycles)	X	
24hour urine for protein measurement	X						X (every 1-3 cycles)	X	
Prescribe lenalidomide via RevAssist®		X					X		
Serum for FreeLite Testing	x						X (every 1-3 cycles)	X	
Dispense study drug for next cycle		X					X		
Perform drug accountability			X				X	X	
Survival status									X 

1. A repeat bone marrow biopsy will only be done at time of suspected complete remission to document complete remission per standard clinical practice and at physician discretion.
2. To include Na, K, Cl, Co2, Ca, Mg, Phosphorous, BUN, Cr., glucose, albumin, alk phos, total Bili, ast/alt.
3. WBC, differential, Hgb, Hct and platelet count
4. Screening CBC and Chemistry parameters need to meet criteria to initiate dosing in section 3.1 within 5 days of starting protocol directed therapy.
5. Pregnancy testing will be done 10-14 days prior to starting therapy and within 24 hours prior of starting lenalidomide on day 1
6. These will be done every 1-3 cycles.

**7. DAY 8 AND DAY 15 (+/- 3 DAYS ASSESSMENTS ARE TO BE DONE DURING CYCLE 1 AND DURING THE CYCLE THE PHYSICIAN DOSE ESCALATES**

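### Staging for the primary PFS endpoint is counted in treatment cycles, so it may slip during holds and progression may be dated somewhat late in patients with more interruptions

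*Combined protocol and SAP*

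**What the plan says.** **Staging.** Section 3.10.1: "Patients will be staged every 1-3 cycles +/- 7 days while on protocol". The flow chart (Section 8.1) gives the same frequency for serum and urine M component, 24-hour urine protein and FreeLite, under Day 1 of the cycles after cycle 1. Skeletal survey and plasmacytoma assessment are done as clinically indicated. Repeat marrow is for suspected complete remission and at physician discretion.

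**Cycle length and breaks.** Section 3.1: "Each cycle will be defined as a 28 day cycle", and "Drug holidays and break in therapy including those due to holidays, physician discretion and drug delivery are allowed as needed". No maximum length is given for these breaks.

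**Cycle delays.** Section 3.3.3.1: "If the patient fails to meet the above-cited criteria for initiation of the next cycle of treatment, dosing should be delayed until recovery". The limit follows: "The maximum delay before treatment should be discontinued will be 6 weeks or at the discretion of the Principal Investigator".

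**Endpoint.** Section 5 has PFS "defined as the time from autologous stem cell transplantation (ASCT) to the time of clinical progression, death, whichever occurs first". It is judged against the assumption that "patients treated with the current standard regimens had a median PFS of 40 months", with a target gain of 12 months.

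No section sets a calendar date for staging, asks for staging during a hold, or says how to date progression first seen after a long gap.

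**The concern.** Progression that shows only in M-protein or light chains is dated when the test is done. If tests fall due by cycle number and the cycle count stops during a hold, the next test moves back by the length of the hold. The error then depends on how much treatment a patient receives: those with the most interruptions may be looked at least often. It runs one way, towards longer PFS and a futility rule that is slower to stop. With a single arm and a historical benchmark, no concurrent control group shares the delay.

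**Working it through.** **1. Planned gaps between stagings** (28-day cycle, three-cycle maximum, 6-week nominal delay)
- No hold: 3 × 28 = 84 days.
- One 6-week hold per three cycles: 84 + 42 = 126 days.
- Two such holds: 84 + 84 = 168 days.
- A 6-week hold before each of three cycles: 3 × (28 + 42) = 210 days.

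**2. Reproducing Table 1.** Section 5 gives the priors IG(100, 3960) for the standard median Ms and IG(3, 80) for the experimental median Me. With d events, the posterior for Me is IG(3 + d, 80 + ln 2 × total follow-up). The trial stops if Pr(Me > Ms + 12 | data) < 0.035. I simulated 48 patients accruing at 2 per month with exact event dates, 8,000 runs per scenario. Looks were every 6 months during accrual, plus one 48 months after the last patient.

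| True median (months) | 30 | 36 | 40 | 48 | 52 | 60 |
|---|---|---|---|---|---|---|
| Table 1, Pr(stop early) | 0.92 | 0.64 | 0.41 | 0.16 | 0.091 | 0.053 |
| Recomputed | 0.911 | 0.627 | 0.422 | 0.160 | 0.100 | 0.049 |

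All agree within 2 percentage points. Six-monthly looks through the whole of follow-up do not fit (0.535 at 40 months and 0.144 at 52, from 1,000 runs), so the look schedule above is an inference from the table.

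**3. Adding late dating.** Each progression is moved to the next staging visit, and a patient not yet dated as progressed counts as event-free up to the look. There were 4,000 runs per scenario. The hold patterns are assumptions. For gaps G between stagings, the mean lag should be about E[G²] / (2 E[G]), at 30.4375 days per month:
- 84 days throughout: 84 / 2 = 42 days = 1.38 months.
- 25% of gaps at 126 days: E[G] = 94.5 and E[G²] = 0.75 × 7,056 + 0.25 × 15,876 = 9,261. The lag is 9,261 / 189 = 49 days = 1.61 months.
- All gaps at 168 days: 168 / 2 = 84 days = 2.76 months.

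The simulation agrees:

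| Pattern on 84-day staging | Mean lag (months) | Excess over no hold | Pr(stop), true 40 | Pr(stop), true 52 |
|---|---|---|---|---|
| No hold | 1.39 | – | 0.314 | 0.057 |
| 25% of intervals +42 days | 1.62 | 0.23 | 0.299 | 0.049 |
| 25% of intervals +84 days | 1.95 | 0.56 | 0.273 | 0.040 |
| All intervals +42 days | 2.10 | 0.71 | 0.263 | 0.036 |
| 25% of intervals +168 days | 2.78 | 1.39 | 0.220 | 0.027 |
| All intervals +84 days | 2.79 | 1.40 | 0.209 | 0.025 |

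For comparison, exact dating gave 0.417 and 0.097, and undelayed 28-day staging gave a lag of 0.46 month with 0.396 and 0.083.

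**4. The part due to holds.**
- Lag: 1.62 − 1.39 = 0.23 month, up to 2.79 − 1.39 = 1.40 months.
- Stopping at a true 40 months: 0.314 − 0.299 = 0.015, up to 0.314 − 0.209 = 0.105.
- The drop from 0.417 to 0.314 is the ordinary lag of 84-day staging and is not caused by holds.

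The simulation starts the staging grid at the PFS origin and so ignores the 60 to 180 days between transplant and first dose.

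**The case against.** **The text does not forbid staging during a hold.** Section 3.10.1 says on protocol, not on treatment, and a within-cycle hold or short holiday need not move Day 1. This stands. The slip is permitted, not prescribed, and a reader who infers that held patients go unstaged goes further than the documents.

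**Most of the lag is ordinary visit lag.** A reader might take the 210-day gap, with an observed median of 43.4 months for a true 40, and call the bias 3.4 months, or about 29% of the 12-month target (3.44 / 12). The documents do not support that as the effect of holds. Undelayed 84-day staging already gives 41.4 months, so holds account for about 2.1 months (43.44 − 41.36) even then. That case also needs every patient delayed 6 weeks before every cycle, although Section 3.3.3.1 suggests considering dose reduction after more than 4 weeks.

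**The historical figure may carry the same lag.** Sections 1.1 and 1.4 describe two maintenance trials with medians of about 40 months. Their progression dates presumably also depended on visits, but their schedules are not in the documents. The net bias from ordinary lag is therefore unknown and may be small.

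**Not every event waits for staging.** Deaths count in PFS and are not dated by staging. New bone lesions, plasmacytomas and hypercalcaemia also count (Section 3.9) and can surface clinically. Calcium is in the chemistry panel, which is not limited to one to three cycles, though it too is listed under cycle Day 1. This stands and makes the figures above lean high.

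**Conclusion.** The gap in wording is real. Staging is counted in cycles, cycle starts can move without a firm limit, and nothing ties staging to the calendar. Progression may therefore be dated later in patients with more interruptions, always towards longer PFS. The added effect is modest: about 0.2 to 1.4 months under the assumed patterns, or 2% to 12% of the 12-month target (0.23 / 12 and 1.40 / 12). The chance of stopping a regimen with a true 40-month median falls by about 1.5 to 10.5 percentage points.

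The estimate rests on assumed hold rates, exponential PFS, three-cycle staging for every patient, and every event being found only at staging. The first could move it either way; the last two push it up. Confidence is high for the gap in the text and lower for its size. It would be wrong to infer that the PFS comparison is invalid, or that calendar staging would remove all of the lag.

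**What to change.** In Section 3.10.1 and the flow chart, schedule serum and urine M-protein and FreeLite testing by calendar from Cycle 1 Day 1. Require it at least every 12 weeks (+/- 7 days) while the patient is on protocol and progression-free, regardless of dose holds, cycle delays or drug holidays. Extra stagings stay at physician discretion. Twelve weeks is 84 days, the present three-cycle maximum for an undelayed patient, so no planned interval becomes longer and no dosing, hold or discontinuation rule changes.

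The cost is a change of wording and a few routine blood and urine tests that fall during holds. The change removes the excess lag due to holds and keeps the ordinary lag of about 1.4 months. It should be worded to cover patients on hold but not those who have ended therapy. Under Section 4.3 the latter have contact every 6 months, and extending 12-week staging to them would be a larger commitment that this point does not ask for.
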